5.4 Dose Reduction, Delay and Discontinuation

Toxicity necessitating dose modification or delay is based on NCI CTCAE v 4.03 Toxicity Grade. The Principal Investigator will assess whether each AE is related or not to each of the study drugs. Events that are judged definitely, probably or possibly related are considered related AEs. Events that are considered unlikely or definitely not related are considered not related AEs. Factors to be taken into consideration include the temporal relationship between administration of study drug and the onset of the AE, other potential causes of the AE including the subject's underlying medical condition and concomitant medications, whether the AE is consistent with known AEs previously attributed to a study drug, whether the AE decreases or resolves upon withholding or reducing the dose of the study drug, or whether the AE recurs upon reintroduction of the study drug. AEs defined below (Sections 5.4.1), unless the Principal Investigator considers the event clearly unrelated to study drug, will be considered a toxicity that necessitates dose modification or delay.

5.4.1 Toxicities Necessitating Dose Modification or Delay

Toxicities necessitating dose modification or delay will be defined as any non-hematologic or hematologic toxicity listed below. Study treatment should be discontinued in the event of a toxicity lasting more than 28 days despite appropriate medical management, unless reviewed and approved by the Principal Investigator. The action in Table 3 should be taken for the following toxicities:

Proprietary Information of MD Anderson

Non-hematologic toxicity will be defined as any of the following:

- Any unmanageable Grade 3 or 4 non-hematologic toxicity with failure to improve (< Grade 2) or recover to baseline within 14 days of withholding drug
- Grade 3 or 4 non-blistering rash that does not resolve to < Grade 2 within 14 days
- Any desquamating (blistering) rash
- Any grade Stevens-Johnson syndrome or toxic epidermal necrolysis
- Grade 3 or 4 thrombosis/embolism
- Grade 3 or 4 peripheral neuropathy which began or worsened while on study

Hematologic toxicity will be defined as any of the following:

- Grade 3 neutropenia with infection or fever (single temperature of > 38.3 °C, or with a sustained temperature of ≥ 38 °C lasting > 1 hour).
- Grade 4 neutropenia (ANC<500/µL) lasting > 7 days.
- Grade 4 thrombocytopenia (<25,000/µL)

The following action should be taken for any unmanageable toxicity that is consistent with the rules outlined above:

Table 3. Dose modification for toxicity

Toxicity Grade	Action to be Taken
Grade 3 neutropenia associated with fever (single temperature of > 38.3 °C, or with a sustained temperature of ≥ 38 °C lasting > 1 hour)	
• Hold lenalidomide and ibrutinib.• Follow CBC weekly.• If neutropenia has resolved to < Grade 2 prior to Day 21 of the current cycle, restart lenalidomide at next lower dose level, (see Table 5) and continue through the scheduled Day 21 of the current cycle. Otherwise, omit for remainder of cycle and reduce the dose of lenalidomide by 1 dose level at the start of the next cycle.
OR	
• Withhold ibrutinib until recovery to < Grade 2 or baseline; may restart at original dose level for the first occurrence. For subsequent occurrence, please refer to Table 4 for next lower dose level.• Withhold rituximab until recovery to < Grade 2 or baseline.• Omitted doses are not made up.• G-CSF may be used
≥ Grade 4 thrombocytopenia	
• Hold lenalidomide and ibrutinib dose.• Follow CBC weekly.• If thrombocytopenia resolves to < Grade 2 prior to Day 21 of the current cycle, restart lenalidomide at next lower dose

Proprietary Information of MD Anderson

	
level and continue through the scheduled Day 21 of the current cycle. Otherwise, omit for remainder of cycle and reduce the dose of lenalidomide by 1 dose level at the start of the next cycle.
 
Withhold ibrutinib until recovery to < Grade 2 or baseline; may restart at original dose level for the first occurrence. For subsequent occurrence, please refer to Table 4 for next lower dose level.Withhold rituximab until recovery to < Grade 2 or baseline.Omitted doses are not made up.Hold prophylactic anti-coagulation including aspirin, if applicable.Restart prophylactic anti-coagulation and/or aspirin when platelet count is $\geq 50,000/\text{mm}^3$.
Non-blistering rash Grade ≥ 3	
If Grade ≥ 3, hold lenalidomide and ibrutinib dose. Follow weekly. If the toxicity resolves to < Grade 2 prior to Day 21 of the current cycle, restart lenalidomide at original dose level (for first occurrence) and continue through the scheduled Day 21 of the current cycle. Otherwise, omit for remainder of cycle.Omitted doses are not made up.For the second occurrence of Grade ≥ 3, hold lenalidomide, and follow weekly. If the toxicity resolves to \leq Grade 2 prior to Day 21 of the current cycle, restart lenalidomide at next lower dose level and continue through the scheduled Day 21 of the current cycle. Otherwise, omit for remainder of cycle and reduce the dose of lenalidomide by 1 dose level at the start of the next cycle. Omitted doses are not made up.Withhold ibrutinib until recovery to Grade ≤ 1 or baseline; may restart at original dose level for the first occurrence. For subsequent occurrence, please refer to Table 4 for next lower dose level.Treatment with 10mg of prednisone or equivalent for 10 days (with or without taper) and/ or antihistamines PO daily is recommended.If Grade ≥ 3 rash has not improved to at least Grade 1 within 14 days of drug being withheld and administration of 10mg of steroids and/or antihistamines daily, the subject will discontinue study treatment.
Desquamating (blistering) rash Any grade	
Discontinue study drugs. Remove patient from study.Start supportive care: daily antihistamine, 10mg or higher of prednisone or corticosteroid equivalent as clinically indicated

Proprietary Information of MD Anderson

≥ Grade 3 thrombosis/embolism	
Hold lenalidomide and start therapeutic anticoagulation with low molecular weight heparin, if appropriate. Warfarin anticoagulation is not allowed.Restart lenalidomide at investigator's discretion (maintain dose level) after anticoagulation is initiated.See anticoagulation considerations, Section 6.1.2.2.
Peripheral neuropathy	
If Grade 3, hold lenalidomide dose. Follow at least weekly.If the toxicity resolves to ≤ grade 1 prior to Day 21 of the current cycle, restart lenalidomide at next lower dose level and continue through the scheduled Day 21 of the current cycle. Otherwise, omit for remainder of cycle and reduce the dose of lenalidomide by 1 dose level at the start of the next cycle. Omitted doses are not made up.
Grade 3	
Grade 4	
If Grade 4, discontinue lenalidomide. Remove patient from study.
Other non-hematologic toxicity ≥ Grade 3	
Hold lenalidomide and ibrutinib dose. Follow at least weekly.If the toxicity resolves to < Grade 2 prior to Day 21 of the current cycle, restart lenalidomide and continue through the scheduled Day 21 of the current cycle. Otherwise, omit for remainder of cycle. Omitted doses are not made up. For toxicity attributed to lenalidomide, reduce the lenalidomide dose by 1 dose level when restarting lenalidomide.Withhold ibrutinib until recovery to Grade ≤1 or baseline; may restart at original dose level for the first occurrence. For subsequent occurrence, please refer to Table 4 for next lower dose level.Withhold rituximab until recovery to < Grade 2 or baseline.

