Non-hematologic dose-limiting toxicity was defined as any of the following: any Grade 3 or 4 non-hematologic toxicity (excluding: Grade 3 rash that resolves to < Grade 2 within 10 days with systemic corticosteroid treatment, fatigue, anorexia, nausea, fever without neutropenia, tumor lysis syndrome); grade 3 rash that does not resolve to < Grade 2 within 10 days with corticosteroid treatment; any grade Stevens-Johnson syndrome or toxic epidermal necrolysis; grade 3-4 bullous dermatitis; failure of any Grade 3 or 4 non-hematologic toxicity (as defined above) to resolve or recover to baseline level after delaying the next dose by more than 2 weeks; AST or ALT ≥ 3 x ULN in combination with a total bilirubin ≥ 2 x ULN. Hematologic dose-limiting toxicity was defined as any of the following: any Grade 4 hematologic toxicity, except for grade 4 neutropenia ≤ 7 days; grade 4 neutropenia > 7 days; grade 3 or

Proprietary Information of MD Anderson

4 neutropenia complicated by fever $\geq 38.5^{\circ}\text{C}$ or infection; grade 4 thrombocytopenia (must be repeated same day by a separate peripheral blood draw to confirm toxicity); grade 2-3 thrombocytopenia complicated by hemorrhage.

The preliminary safety data that has not been reported or published suggests the combination is tolerable. Of 22 subjects, 8 developed a Grade 1 or 2 rash, and 8 subjects developed a Grade 3 rash; rash was not considered a DLT in this study unless the rash did not resolve to < Grade 2 within 10 days with corticosteroid treatment. In addition, rash was associated with allopurinol in several cases and with Bactrim (sulfamethoxazole and trimethoprim) in 1 case. No cytokine storm reactions were seen. As a result of this approach, in the CTEP/A051103 study, no DLTs were seen and no MTD was identified. The rashes were manageable with temporary holding of ibrutinib and lenalidomide, concomitant therapy with corticosteroids and/or antihistamines, and discontinuation of potential contributors such as allopurinol if applicable. The maximum dose of lenalidomide given was the highest planned dose of 20 mg.

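### The Section 5.4.1 trigger list and Table 3 contradict each other on non-hematologic toxicity and rash, and the list does not name febrile or infected Grade 4 neutropenia lasting 7 days or less

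*Combined protocol and SAP*

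**What the plan says.** Section 5.4 treats the events defined in Section 5.4.1 as the ones that call for dose modification or delay, unless the Principal Investigator judges them clearly unrelated. Section 5.4.1 gives a list of those events and then Table 3, introduced by: "The following action should be taken for any unmanageable toxicity that is consistent with the rules outlined above".

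- **General non-hematologic toxicity.** The list requires an unmanageable Grade 3 or 4 event with "failure to improve (< Grade 2) or recover to baseline within 14 days of withholding drug". The Table 3 row for other non-hematologic toxicity of Grade 3 or above has no 14-day condition and begins: "Hold lenalidomide and ibrutinib dose. Follow at least weekly".
- **Non-blistering rash.** The list requires a Grade 3 or 4 rash still at Grade 2 or worse after 14 days. The Table 3 row holds both oral drugs at Grade 3 or above, again without a waiting period.
- **Neutropenia.** The list has two items: "Grade 3 neutropenia with infection or fever" and "Grade 4 neutropenia (ANC<500/µL) lasting > 7 days". The Table 3 row is labelled "Grade 3 neutropenia associated with fever", with a temperature definition, then the word OR. In the text available for this review nothing follows OR in the label column.
- **Drug sections.** Section 5.4.2 ties the ibrutinib hold to the rules of Section 5.4.1 and then sends the dose change to Table 3. Sections 5.4.3 and 5.4.4 tie rituximab and lenalidomide holds to Table 3.

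**The concern.** The list decides whether Table 3 applies, so the two must use the same condition for the same event. For general non-hematologic toxicity they do not. The list counts an event only after drug has been withheld for 14 days without recovery, yet the instruction to withhold drug is the first step of the table that the list is meant to open. The neutropenia items leave a different difficulty: a complication that is listed at Grade 3 is not listed at Grade 4 when the neutropenia is short.

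At stake is consistent handling of severe toxicity in a three-drug combination that Section 9.6 says few patients have received. Section 3.2.2 also makes the frequency of adverse events requiring discontinuation or dose reduction a safety endpoint, and Section 9.3.1 summarises the number of dose modifications. Both counts depend on which trigger a clinician follows.

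**Working it through.** No sample size, power or error rate is involved, and the plan gives no figure to reproduce. The check sets the passages side by side.

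**1. General non-hematologic toxicity.** Take a Grade 3 event, attributed to lenalidomide, that would clear after ten days off drug.

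- By the list: it has not failed to recover within 14 days of withholding, so it is not a trigger and nothing in the list calls for a hold.
- By the Table 3 row: lenalidomide and ibrutinib are held at once, rituximab is withheld until recovery, and lenalidomide restarts one level lower.

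The same result holds at Grade 4, so this is not a matter of worse events being treated more lightly. It is a circular condition: the hold must have happened before the rule that orders it can apply.

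**2. Non-blistering rash.** The list waits for non-resolution within 14 days, while the table acts at Grade 3 or above. The same table row ends study treatment if the rash has not improved to Grade 1 within 14 days of withholding drug and giving steroids or antihistamines. The list condition therefore lies close to the row's discontinuation step rather than its opening hold. By contrast, thrombosis, neuropathy and thrombocytopenia carry matching grade thresholds in list and table.

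**3. Routing by drug.** If Section 5.4.2 is read as pointing to the list, the event in step 1 does not hold ibrutinib, but it does hold lenalidomide and rituximab through Sections 5.4.3 and 5.4.4.

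**4. Neutropenia, by the list alone.**

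| Event | On the 5.4.1 list? |
|---|---|
| Grade 3 with fever or infection | Yes |
| Grade 4, more than 7 days, with or without fever | Yes |
| Grade 4, 7 days or less, no fever or infection | No |
| Grade 4, 7 days or less, with fever or infection | No |

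The Grade 3 item is hard to read as Grade 3 or higher. The same list names both grades for rash, thrombosis and neuropathy, and Table 3 uses the greater-or-equal sign where it means a minimum grade. The phase 1 definition reported in Section 1 covers grade 3 or grade "4 neutropenia complicated by fever" or infection, separately from prolonged Grade 4 neutropenia. One further difference: the list item covers infection or fever, but the visible Table 3 label mentions fever only.

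**5. Scale.** Inputs: 60 planned patients (Section 4.1); in the earlier lenalidomide-rituximab study, Grade 4 neutropenia 10% and febrile neutropenia under 1% (Section 1). If those rates carried over:

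- all Grade 4 neutropenia: 60 × 0.10 = 6 patients;
- febrile neutropenia: fewer than 60 × 0.01 = 0.6, so fewer than 1 patient.

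The event in the last row of the table, where febrile, is a subset of the second figure, not the first. The documents give no rate for the three-drug combination and none for afebrile infection with Grade 4 neutropenia.

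**The case against.** The strongest objection is that Table 3 may already settle everything. It orders a hold for any other non-hematologic event of Grade 3 or above, Sections 5.4.3 and 5.4.4 go straight to it, Section 5.4.2 refers to it for dose changes, and it sits inside Section 5.4.1. A clinician who starts from the table would hold drug. This stands as a limit: on point 1 the documents show a contradiction, not an absence of any rule. It does not remove the contradiction, because the table's own introduction confines it to toxicities that fit the list. Both the list item and that introduction also require the toxicity to be unmanageable, which narrows the events concerned but leaves the 14-day mismatch.

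On neutropenia, a reader might infer that febrile Grade 4 events escape the dose rules altogether. The documents do not support that. The broken Table 3 label may have contained a Grade 4 entry. A recovering Grade 4 count passes through Grade 3, where the listed item applies if fever or infection persists, and an infection of Grade 3 or above could be reached through the general non-hematologic row. The phase 1 wording is a first-cycle dose-limiting toxicity definition from another study; it shows how both grades can be named, but sets no standard here.

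A reader might also infer that study sites would diverge. Section 3.1 describes a single-center trial, so the possible inconsistency is between treating clinicians or between patients. Finally, the affected endpoint is descriptive, with no test or threshold. In the general row ibrutinib may restart at its original dose after a first event, and lenalidomide is reduced only when the toxicity is attributed to it, so the effect on the count is limited.

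**Conclusion.** The contradiction between the Section 5.4.1 list and Table 3 is established from the text for general non-hematologic toxicity (Grades 3 and 4 alike) and for non-blistering rash. The split by drug follows if Section 5.4.2 is read literally as pointing to the list. That the list does not name Grade 4 neutropenia with fever or infection of 7 days or less is also established. Whether Table 3 covers that event cannot be determined from the available text.

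The consequence is that clinicians at this center could handle the same event differently, with a bearing on patient safety and on a descriptive safety count. It does not enter the definition of PFS or the sample size. The size of the neutropenia gap cannot be derived for the triplet. The 6 of 60 figure should not be taken as the number affected, since it counts all Grade 4 neutropenia; the only documented febrile rate gives fewer than 1 of 60, on the assumption that the doublet rate carries over.

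**What to change.** Reconcile the Section 5.4.1 list, Table 3 and Sections 5.4.2 to 5.4.4 so that each event has the same trigger wherever it appears. Specifically:

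- for general non-hematologic toxicity and for non-blistering rash, state whether the rule starts at onset of the qualifying grade or after a period without recovery, and use that statement in both the list and the table;
- state explicitly how Grade 4 neutropenia with fever or infection of 7 days or less is handled, check that the full Table 3 neutropenia label agrees, and align the infection and fever wording;
- have the three drug sections refer to the same source for holds.

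Which triggers and actions apply is for the clinical team to decide. The cost is protocol wording, with no added assessments, visits or patients.

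### Table 3 lets lenalidomide restart at Grade 2 after a second severe rash, a grade that the same row's 14-day stop treats as failure

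*Combined protocol and SAP*

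**What the plan says.** All of this is in the combined protocol and SAP, section 5.4.1, mostly in the non-blistering rash row of Table 3.

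- **First Grade 3 or higher rash.** Both oral drugs are held. If the rash falls below Grade 2 before Day 21, the instruction is to "restart lenalidomide at original dose level (for first occurrence".
- **Second Grade 3 or higher rash.** The instruction is to "hold lenalidomide, and follow weekly. If the toxicity resolves to" a stated grade, and it continues "Grade 2 prior to Day 21 of the current cycle, restart lenalidomide at next lower dose level and continue through" the scheduled Day 21. The sign between those two fragments is less-than-or-equal, so Grade 2 itself qualifies.
- **Ibrutinib, same row.** It is withheld until the rash is at or below Grade "1 or baseline; may restart at original dose level for the first occurrence".
- **Rash treatment.** "Treatment with 10mg of prednisone or equivalent for 10 days (with or without taper) and/ or antihistamines PO daily is recommended".
- **Stop.** Study treatment ends if a rash of Grade 3 or higher "has not improved to at least Grade 1 within 14 days of drug being withheld and administration of 10mg of steroids and/or antihistamines", taken each day. The bullet does not distinguish first from later occurrences.

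Among the toxicities that call for action, section 5.4.1 lists "Grade 3 or 4 non-blistering rash that does not resolve to < Grade 2 within 14 days". That again puts the line below Grade 2.

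**The concern.** A recurrent severe rash needs less recovery before lenalidomide is resumed than a first one does, and the plan gives no reason. Within one row, Grade 2 is good enough to restart lenalidomide, not good enough to restart ibrutinib, and bad enough at 14 days to end study treatment.

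What is at stake is the safety of individual patients. Someone held for a second severe rash can be re-exposed while the rash is still Grade 2, then taken off treatment at the next weekly check because it is still Grade 2. Discontinuations and dose reductions because of adverse events are also a listed safety endpoint (section 3.2.2), so the handling of these patients enters the tolerability results. Two-year PFS and its analysis do not depend on this rule.

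**Working it through.** No figure in the plan needs reproducing. The check has two parts: compare the restart thresholds, then count days.

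**1. Same-cycle lenalidomide restart rules in Table 3 that name a grade**

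| Toxicity | Grade needed to restart | Restart dose | Grade 2 allowed? |
|---|---|---|---|
| Neutropenia | below 2 | one level lower | no |
| Thrombocytopenia | below 2 | one level lower | no |
| Rash, first | below 2 | original | no |
| Rash, second | 2 or below | one level lower | **yes** |
| Neuropathy, Grade 3 | 1 or below | one level lower | no |
| Other non-hematologic | below 2 | one level lower if attributed to lenalidomide | no |

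The neuropathy rule reads at or below "grade 1 prior to Day 21 of the current cycle, restart lenalidomide at next lower dose level". Five of the six rules exclude Grade 2. Three of those five (neutropenia, thrombocytopenia, neuropathy) always restart one level lower, so a reduced dose is not what sets the second-rash rule apart. The thrombosis row names no grade and is left out.

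**2. Grades that satisfy each rash rule**

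- Second-rash restart: Grades 0, 1, 2.
- Stop at 14 days (treated rash): Grade 2 or higher.
- Common to both: Grade 2.

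**3. When the two rules meet**

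Let the hold begin on cycle day d. Assume weekly checks on days d+7 and d+14. Restart must come before Day 21, that is, by Day 20.

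- Both checks in time: d + 14 ≤ 20, so d ≤ 6. For d = 1 to 6 the second check falls on Days 15 to 20, exactly at the 14-day limit. A treated second rash that first reaches Grade 2 at that check meets both the restart rule and the stop rule.
- First check only: d + 7 ≤ 20, so d ≤ 13. For d = 7 to 13 the check falls on Days 14 to 20 and the stop on Days 21 to 27. Lenalidomide can restart at Grade 2 seven days before the stop falls due, with ibrutinib still withheld. The same happens for d = 1 to 6 if Grade 2 is reached at the first check.
- For d ≥ 14, d + 7 ≥ 21, so no scheduled check comes in time for a same-cycle restart.

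**4. After the correction**

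If restart requires below Grade 2, the restart grades are 0 and 1. The stop grades are still 2 and above. No grade satisfies both.

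**The case against.** The strongest reply is that the row already has a safe answer. The stop is mandatory and has no exception, and nothing in the restart bullet claims to suspend it. That is right. A reader might infer that the plan leaves open which instruction governs, so that two physicians could properly treat the same patient in opposite ways. The text does not support that: a treated rash still at Grade 2 on day 14 ends study treatment, whether or not lenalidomide was resumed a week earlier. What remains is that the restart rule permits re-exposure at a grade the row itself counts as failure.

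A second reply is that the looser grade may be a deliberate trade against the lower dose, since a first rash restarts at full dose. The table above weakens this, because three other rules lower the dose and still exclude Grade 2. A drafting slip is at least as plausible.

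Third, the comparison covers same-cycle restarts only. Where recovery comes too late, the fallback of omitting the rest of the cycle and resuming lower in the next one names no grade. This limits the point's reach but does not explain the outlier.

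Fourth, the direct overlap is narrow. It needs a second Grade 3 or higher rash, steroid or antihistamine treatment (recommended, not required), a hold begun on Days 1 to 6, no earlier fall to Grade 2, and exactly Grade 2 at day 14. The weekly instruction does not fix the check days either. All of this stands, and it bears on size.

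Finally, a reader might project patient numbers from the phase 1 study of the combination (section 1), where 8 of 22 had Grade 3 rash: 8/22 = 36%, and 0.364 × 60 = about 22. That would count first rashes, not second ones. It comes from mixed dose levels, and several of the rashes were linked to allopurinol and one to Bactrim, which can be withdrawn. Section 1 also gives 7% Grade 3 rash for lenalidomide and rituximab without ibrutinib. The documents give no recurrence rate, so no count of affected patients can be supported.

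**Conclusion.** The point holds as an error in one threshold. After a second Grade 3 or higher rash, Table 3 allows lenalidomide back at Grade 2. Its five other graded same-cycle restart rules forbid this, ibrutinib in the same row waits for Grade 1 or baseline, and the row's own 14-day stop treats Grade 2 as failure. For holds begun on Days 1 to 6 both rules can be met at the 14-day point. For earlier easing, or holds begun on Days 7 to 13, the patient can be re-exposed a week before the stop is due.

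The day ranges assume checks at exactly 7 and 14 days after the hold. The conflict with the stop also assumes that the rash was treated as the row recommends. Few patients are likely to be affected, and the number cannot be estimated from the documents. The sample size and the primary analysis are unaffected. It is a small correction, but worth making because it concerns re-exposure after a recurrent severe toxicity.

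**What to change.** In the second-occurrence bullet of the non-blistering rash row, change the less-than-or-equal sign before Grade 2 to less-than. That brings the bullet into line with the first-occurrence rule and removes the conflict. Optionally, and only as a clarification, add a sentence saying that the 14-day stop still applies at a second occurrence.

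The drafting cost is one symbol. The clinical cost falls on a few patients whose second rash sits at Grade 2: they wait longer for lenalidomide or miss the rest of that cycle's doses. On daily dosing with weekly checks, the earliest restart now possible is Day 8 (d = 1), so at most 21 − 8 + 1 = 14 reduced daily doses are forgone in that cycle. The start of the next cycle is one dose level lower under either wording.

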7.3 Follow-up Phase

The follow up period will start at the end of treatment visit (after cycle 12) Patients will be followed every 12 weeks (\pm 2 weeks) for the first year and then every 24 weeks (\pm 4 weeks) up to the end of the follow up period, 3 years after the last subject's last study drug dose.

For patients who have completed treatment the follow up assessments will include:

- Physical exam including vital signs and ECOG PS
- Clinical laboratory tests for hematology and serum chemistry
- Second primary malignancy (SPM)
- Adverse events and hospitalization up to 30 days after last study drug
- Overall survival
- Radiologic assessment (CT, PET/CT, or MRI)
- Research laboratory blood samples at PD only.

For patients who discontinue treatment due to progressive disease or relapse, follow up assessments will include:

- Overall survival
- Subsequent anti-lymphoma therapy (including the time of initiation of therapy and best response to first subsequent anti-lymphoma treatment utilized after discontinuation from this study)
- Adverse events and hospitalization up to 30 days after last study drug (Safety visit)
- SPM

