8.2 Treatment Discontinuation

Proprietary Information of MD Anderson

Study treatment will be discontinued in any of the following events:

- Confirmed PD
- Unacceptable toxicity: an intercurrent illness or AE that prevents further study drug administration beyond 28 days
- Treatment discontinuation by subject beyond 28 days
- Investigator decision
- Subject becomes pregnant

All subjects, regardless of reason for discontinuation of study treatment will undergo a treatment termination visit and followed for progression and survival.

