8.3 Study Exit/Withdrawal

Exit from study (including all follow up) will occur under the following circumstances:

- Withdrawal of consent for follow-up observation by the subject
- Lost to follow up
- Study termination by the Investigator
- Death

If a subject is lost to follow up, every reasonable effort should be made by the study personnel to contact the subject. The measures taken should be documented.

When a subject withdraws before the completing the study, the following information should be documented:

- Reason for withdrawal
- Whether the subject withdraws full consent (withdraws consent for treatment and all follow up including further contact) or partial consent (withdraws consent to treatment but agrees to participate in follow up visits).

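### Table 3 removes patients with two toxicities from the study, against Sections 8.2, 8.3 and 9.5; read literally, it would censor their PFS and OS for a treatment-related reason

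*Combined protocol and SAP*

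**What the plan says.** Section 5.4.1, Table 3, orders removal from the study in exactly two rows. For blistering rash of any grade the action is "Discontinue study drugs. Remove patient from study". For Grade 4 peripheral neuropathy it is "discontinue lenalidomide. Remove patient from study". Elsewhere in the same table, a non-blistering rash of Grade 3 or higher that does not improve leads to a different outcome: "the subject will discontinue study treatment".

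Section 8.2 says: "All subjects, regardless of reason for discontinuation of study treatment will undergo a treatment termination visit and followed for progression and survival". Section 8.3 opens with "Exit from study (including all follow up) will occur under the following circumstances" and gives four circumstances: withdrawal of consent, loss to follow-up, termination of the study by the investigator, and death.

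Footnote b of the flow chart (Appendix 13.1) asks for disease monitoring to continue in patients who stop therapy without progression. Section 9.5 plans three years of follow-up for every patient unless death comes first.

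Section 7.3 gives two lists of follow-up assessments. One is for patients who completed treatment and includes imaging. The other begins "For patients who discontinue treatment due to progressive disease or relapse, follow up assessments will include". Patients who stop for toxicity without progression are in neither list.

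**The concern.** Table 3 and Section 8.2 cannot both be obeyed if removal from the study means what Section 8.3 says exit means. Table 3 distinguishes stopping treatment from leaving the study, so a literal reading is not far-fetched.

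The primary endpoint is at stake. The 2-year PFS rate is a Kaplan-Meier estimate in all treated patients. Section 9.3.2.1 censors event-free patients at last follow-up, Section 9.4 at the last tumor assessment, and Section 9.3.3 censors OS at last contact. None of these has a separate rule for patients removed for toxicity. Such patients would be censored for a reason tied to the treatment, after therapy was cut short, so the usual assumption that censored patients carry the same risk as those still followed is doubtful. Reports of second primary malignancy during follow-up (Section 10.2.2.3) would be lost as well.

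**Working it through.** **The plan's own figure.** Section 9.5 gives N = 60, an expected 2-year PFS of 77% and a two-sided 95% half-width of 0.106. The normal approximation gives 1.96 × √(0.77 × 0.23 / 60) = 0.1065, which agrees. That figure is not in dispute.

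**The passages side by side.**

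| Place | Status of a patient who stops for one of the two toxicities |
|---|---|
| Table 3, two rows | removed from the study |
| Section 8.2 | followed for progression and survival |
| Section 8.3 | toxicity is not a ground for exit |
| Footnote b | disease monitoring continues if there is no progression |
| Section 7.2.10 | response evaluation at early termination, then on the follow-up schedule until progression |
| Section 7.3 | not listed |
| Section 9.5 | three years of follow-up unless death comes first |

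Table 3 is the outlier, and Section 7.3 is silent.

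**Size if Table 3 is applied literally.** The documents do not say how often either toxicity is expected, so the following are assumptions: k of the 60 patients are removed early without a PFS event, their true 2-year PFS is q, and it is 77% in the other 60 − k. Kaplan-Meier then reports about 77%, while the true all-treated rate is

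((60 − k) × 0.77 + k × q) / 60,

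so the overstatement is k × (0.77 − q) / 60.

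| k | q = 50% | q = 30% |
|---|---|---|
| 0 | 0 | 0 |
| 1 | 1 × 0.27 / 60 = 0.45 points | 1 × 0.47 / 60 = 0.78 points |
| 2 | 2 × 0.27 / 60 = 0.90 points | 2 × 0.47 / 60 = 1.57 points |
| 3 | 3 × 0.27 / 60 = 1.35 points | 3 × 0.47 / 60 = 2.35 points |

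For k = 3 the true rate would be 75.65% (q = 50%) or 74.65% (q = 30%).

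**Bounds without an assumption on q, for k = 3.** If all three progress by 2 years, the true rate is 57 × 0.77 / 60 = 73.15%, and Kaplan-Meier overstates it by 3.85 points. If none progresses, the true rate is (57 × 0.77 + 3) / 60 = 78.15%, and Kaplan-Meier understates it by 1.15 points. The sign therefore depends on how the removed patients fare.

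**Precision.** With 57 patients left, the half-width is 1.96 × √(0.77 × 0.23 / 57) = 0.109, against 0.1065 with all 60. Possible bias matters more here than lost precision.

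**The case against.** The strongest reply is that retention is already required by Section 8.2, footnote b, Section 7.2.10 and Section 9.5, and that Section 8.3 does not allow exit for toxicity. A site that follows those sections loses nothing. The protocol also uses the word study loosely: Section 5.6 lists a patient's decision to withdraw from the study among the grounds for stopping treatment. On that view, Table 3, which deals with dose modification, means off treatment. This stands to the extent that the loss is conditional. It does not remove the conflict, because Table 3 uses separate wording when it means treatment only.

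The events may also be rare. Section 1 reports peripheral neuropathy under lenalidomide and rituximab only among Grade 1 or 2 events. In the phase 1 study of the three drugs (22 patients), Stevens-Johnson syndrome or toxic epidermal necrolysis of any grade and Grade 3 or 4 bullous dermatitis counted as dose-limiting, and no dose-limiting toxicity was seen. That window covered the first cycle only and did not count low-grade blistering, so it does not show a rate of zero. It is, however, a good reason to include 0 and 1 in the range of removals. Section 7.2.8 also calls for imaging at early termination, so progression already present at that point would be captured.

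A reader might infer that these patients' outcomes will be lost and that the censoring favours the regimen. The documents support neither as a firm statement. The loss depends on a literal reading of two table cells, and the direction is plausible but not shown.

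**Conclusion.** The contradiction is real and confined to two rows of Table 3, with a matching gap in Section 7.3. Applied literally, those rows would censor treated patients for PFS and OS for a treatment-related reason and could bias the all-treated 2-year PFS. Under the stated assumptions (0 to 3 early removals, true 2-year PFS of 30% to 50% in those patients, 77% in the rest), the overstatement is 0 to about 2.4 points, which is small against the 10.6-point half-width. The removal counts and PFS values are illustrations, not figures from the documents. The point is worth correcting because outcomes that are not collected may be unrecoverable at analysis, not because a large bias has been demonstrated.

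**What to change.** Reconcile the two Table 3 rows with Sections 8.2 and 8.3 by stating that these patients remain in scheduled response and survival follow-up. In Section 7.3, add patients who stop for toxicity without progression to the list that includes radiologic assessment, in line with Section 7.2.10 and footnote b.

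Keep this edit to follow-up status. The Grade 4 neuropathy row names only lenalidomide, so its removal instruction may be the only text there that bears on the other two drugs. The sponsor must make clear separately which study drugs that row stops; no clinical rule is proposed here.

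The cost is a wording amendment. Section 8.2, Section 7.2.10 and footnote b already call for the follow-up and scans, so no new procedure is added.
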